1.3 Background

In 2015 established HMN RHF an occupational rehabilitation program for people with BMI above 30 who might be or is on sick leave directly or indirect cause obesity. This program combines work participation and life style changes and exists only in two institutions in Norway. The goal of the program is to increase function and work ability and weight loss. The program is new, and few documents exist on the effect and the correlation between life style changes and work ability. There is also need to question whether obesity is the reason for work absence or is there other factors that affect work ability. This study wants to follow up a group of people who have been participating occupational rehabilitation at Muritunet.

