The primary goal of this trial: What correlation is there between life style changing and work participation after participating in occupational rehabilitation on Muritunet?

Aims of the trial are:

1. Will changes in physical activity, diets, and life quality correlate with work participation?
2. Will changes in physical activity, diets, and return to work self-efficacy correlate with life quality?
3. Will changes in work participation, life quality, and diets correlate with weight changes?
4. What experience the participants as important factors to achieve lifestyle changes and work participation?

Work participation defined in this study is working full time or partial with an employer, permanent or temporary or as a student. The employee has to work coherently in 28 days without to receive social benefits.

Life quality defines in either in a subjective or an objective perspective [29]. In this study, the subjective perspective emphasizes the individual's positive, negative, cognitive and emotional experience that concern life quality.

Diet in this study is the intake of food and liquid that shall ensure a satisfying amount of calories, nutrient and prevent life style diseases.

Physical activity in this study is action made by musculature in a way that it results in increased energy consumption higher than resting.

3 Implementation

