2. T1, six months after the first stay at Muritunet. Data gathered from the journal, from self-reported forms, and from a physical test. The particular data package is; in and out date for the stay, diagnosis, health problems, work status, social benefits, changing in work status, work place, expected work time pr. Week and occupation code, work motivation, income, diet, physical capacity and activity, life quality and overeating behaviour.
3. T2, 12 months after the first stay at Muritunet. Data gathered from the journal, from self-reported forms, and from a physical test. The particular data package is; in and out date for the stay, diagnosis, health problems, work status, social benefits, changing in work status, work place, expected work time pr. Week and occupation code, work motivation, income, diet, physical capacity and activity, life quality and overeating behaviour.
4. T3, Focus group interview, one to four years after the participants finishing their stay at Muritunet.

5. T4, Data collecting from Norwegian patient register (NPR) and National Education database (NUDB). Will be collected once. Data collected are social benefits as sick leave, work assessment allowance, disability benefits, unemployment benefits, diagnosis for sick leave, changing in work employment, work place and expected work time pr. A week and occupation code.

Some participants will return to their work, but some will not. It will lead to variation for my chose of how to design methods and analyze the data material. Different ways will complete each other, and today it is common to use several methods and models in the same study.

Data analysis is chosen on the background of design and approaches. BL, T1, and T2 is a typical quantitative approach and will be analyzed both on its own, but also compared with data collected in T3 and T4. The qualitative interview will have open-ended questions, and the participants will get the opportunity to reflect on themes defined from the data collection earlier in the study.

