3.2 Inclusion and excluding criteria

Participant inclusion criteria; the participants have to be on sick leave or be in danger to be on sick leave because and obesity related problems. The participants have to have a real opportunity for returning to work, full time or part time. The participants have to have a BMI above 30 and be in age between 18 to 67 years old.

Participants excluding criteria;

1. People with a severe eating disorder.
2. People who cannot consent.
3. People with a severe alcohol and drug abuse.
4. People with a severe psychiatric disease.
5. Pregnancy
6. People with a health condition that contraindicates physical activity.
7. People who receive work assessment allowance.
8. People with or wants so seek for disability benefits.
9. People with permanently organized work.

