3.6 Quantitative data collection

Foams register and explain changing in life style factors and work participation. The physical test may say something about the participant's physical capacity. In this study foams and a test will measure conditions that affect socio- economic, demographic and individual factors, their expectation of returning to work, the motivation for working and sick-leave, physical activity, physical and mental health, diet and nutrition, and life quality. Information about the date of the stay, diagnoses, and activity is in the journal at Muritunet.

Areas	Time of data collection	Foams
Employment data	BL	ARR foam, socio-demographic data and work status (Nasjonal kompetansestest for arbeidsretta rehabilitering)
	BL, T1 and T2	Short ARR foam
	BL	Return to work self- efficacy (RTWSE 19) [31]
Health data	BL	High, waist circumference, body fat percentage and fat-free mass kg
	BL, T1, and T2	Weight, BMI
	BL	Diagnoses
	BL	Subjective Health Complaints (SCH 25) [32].
Physical capacity	BL	Step-test with Borg scale CR 10
	BL, T1, and T2	Registration of level of physical activity(Health Directorate)
Quality of life	BL, T1, and T2	Quality of life (15D) [33].
Food habits	BL	Thoughts and feelings about food, body and eating behavior. Survey about Binge eating disorder (EDO)[34].
	BL, T1, and T2	Food behavior registration (Health Directorate)

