3.9 Analyse

The goal of this study is to explore the correlation between life style changing and work participation. Four secondary issues will result in using different ways of analyzing the data material. In this way, each issue can be investigated on their own, but also analyzed with each other.

The primary analyzing approach for this study is multivariate logistics regression analysis with a focus on the correlation between several independent variables (X) and dependent variables (Y). In the main issue Y= work, and X= physical activity (x1), diets (x2) and life quality (x3). Work divides into three categories; a) full time working, b) part time working, c) not working. In the secondary issue, is Y= life quality and X= physical activity (x1), diets (x2), and the belief in managing (x3).

In the quality research, thematic methods will be used to analyze the interviews. This method can catch the significant complexity in the text and is the most usual way to analyze a text in qualitative research. This way of analyzing consist of six steps. 1. Transcribing data, 2. Reading and re-reading the data, 3. Coding, 4. Search after subjects, 5. Define and give a name to the subjects, and 6. Choose to illustrate examples of different issues.

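### The main model in section 3.9 has no term for work status at entry, although entry status is mixed, so the lifestyle–work association can partly reflect who was already working

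*Protocol*

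**What the plan says.** **Main model.** Protocol section 3.9 names logistic regression as the primary approach and sets out "In the main issue Y= work, and X= physical activity (x1), diets (x2) and life quality (x3". The outcome is a status: "Work divides into three categories; a) full time working, b) part time working, c) not working". No other term, stratum or restriction is listed.

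**Who enters.** Section 3.2 requires that "the participants have to be on sick leave or be in danger to be on sick leave". Section 1.3 describes the programme as one for people "who might be or is on sick leave directly or indirect cause obesity". The benefits listed in section 3.15 cover both going back to work and carrying on with it.

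**How work is defined.** Section 2 counts full-time or part-time employment, or being a student, and adds: "The employee has to work coherently in 28 days without to receive social benefits". Someone who never stopped working can meet this.

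**Work as something that changes.** Aim 3 in section 2 asks "Will changes in work participation, life quality, and diets correlate with weight changes". Section 3.6 says "Foams register and explain changing in life style factors and work participation". Section 3.10 sizes the study on a 25 percent increase in work participation, with 51 participants. Section 3.1 expects that "Some participants will return to their work, but some will not".

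**What is collected.** Work status and social benefits are in the baseline data package (section 3.1). The table in section 3.6 lists the ARR form at baseline and its short version at baseline, T1 and T2.

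**The concern.** Entry status is likely to predict later work status strongly, and the eligibility rule makes it vary between participants. The model in section 3.9 ignores it. A person who kept working and a person who returned can fall in the same outcome category, and the model cannot tell whether a lifestyle variable is associated with work itself or with having been at work at the start.

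The stake is the primary goal. If people working at entry change their lifestyle less, a real association can be hidden. If they change more, it is overstated. If their change is the same, the test of no association stays valid, but unexplained variation in the outcome costs power.

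**Working it through.** **1. The plan's own figure.** The 51 participants of section 3.10 cannot be reproduced, because neither the starting work rate nor the share of participants who change status is given. A two-sided McNemar calculation for a 25-point rise gives 51 if 42.5% change status (power 80.0%), 29 at 25% and 61 at 50%. The figure is not disputed here; 51 is used only as the sample size.

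**2. Assumed inputs.** The protocol gives none of the following.
- Share working at entry, p: 10, 20 or 40%.
- Share of these still working later, s: 85 or 95%.
- Work at follow-up = p + 0.25 (section 3.10, read as percentage points).
- Full time: 60% of kept work and 40% of regained work.
- x1–x3 are changes from baseline, in line with Aim 1.
- d is the difference in change between the entry groups, in SD.

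**3. Formulas.** Return rate among those not working at entry = (p + 0.25 − p·s)/(1 − p). Share of follow-up workers already working at entry = p·s/(p + 0.25). For p = 0.20 and s = 0.85 these are 0.28/0.80 = 35.0% and 0.17/0.45 = 37.8%.

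**4. Simulation.** Multinomial logistic model with three predictors, n = 51, 2-df likelihood-ratio test of one predictor. There were 2000 runs per cell (1000 for the Firth fit). Power is for a true odds ratio of 2.5 per SD within entry groups. In the d = 0.4 columns, change is smaller in those working at entry.

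| p / s (%) | Return rate (%) | Already working (%) | Power d=0, without / with term (%) | Power d=0.4, without / with (%) | Firth with term, d=0.4 (%) |
|---|---|---|---|---|---|
| 10 / 85 | 29.4 | 24.3 | 60.3 / 66.0 | 49.9 / 67.2 | 58.8 |
| 10 / 95 | 28.3 | 27.1 | 56.4 / 65.2 | 41.8 / 63.2 | 54.9 |
| 20 / 85 | 35.0 | 37.8 | 60.6 / 68.5 | 43.4 / 69.0 | 61.0 |
| 20 / 95 | 32.5 | 42.2 | 50.1 / 63.5 | 30.9 / 64.1 | 54.0 |
| 40 / 85 | 51.7 | 52.3 | 58.7 / 65.0 | 39.8 / 66.4 | 60.5 |
| 40 / 95 | 45.0 | 58.5 | 44.3 / 58.6 | 21.8 / 59.6 | 49.5 |

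At d = 0 the term adds 5.7 to 14.3 points of power. A repeat run with separate code gave 48–61% against 60–68% at d = 0, and 28–50% against 63–69% at d = 0.4.

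**5. Opposite sign.** With change 0.4 SD larger in those working at entry, the unadjusted test rejects more often: 71–78% against 64–69% with the term. That excess comes from confounding and is not a gain.

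**6. No true association.** Rejection rates without and with the term:
- d = 0: 5.7–7.4% against 7.2–8.3%
- d = 0.4: 8.2–10.5% against 6.9–8.1%
- d = 0.8: 11.8–23.9% against 7.3–9.1%

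The ordinary test is liberal at this size even with the term. The Firth-type penalised fit with the term held 3.5–5.1% at d = 0.4. At 10% working at entry, 4–5% of the penalised fits had not met the iteration tolerance.

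**7. Sparse cells.** The expected number working at entry but not at follow-up is n·p·(1 − s). For p = 10% this is 51 × 0.10 × 0.15 = 0.77, or 51 × 0.10 × 0.05 = 0.26. For p = 40% it is 3.06 or 1.02. The chance that this cell is empty at p = 40% is (1 − 0.06)^51 = 4.3%, or (1 − 0.02)^51 = 35.7%. Simulated rates of any empty cell were 4–5% and 35–37% at p = 40%, and 57–60% and 80–84% at p = 10%.

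**8. Parameters.** The three-category model has 2 × (1 + 3) = 8 parameters without the term and 2 × (1 + 4) = 10 with it.

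**The case against.** **Covariates belong in the analysis plan.** The statistical analysis plan is not shown and section 3.9 does not call its list closed. This lowers the confidence but does not remove the point: the protocol writes out the outcome and predictors of its main model, and that stated model can be judged.

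**The aim is exploratory and work is defined as a state.** Staying in work counts as participation, so an unadjusted association is a legitimate description. A status outcome is indeed not an error in itself. But sections 2, 3.6 and 3.10 also treat work as something that changes, and an unadjusted association cannot be read that way. The odds ratio of 2.5 in the simulation is a within-entry-group value, so the power figures presuppose that target.

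**Most entrants may be off work.** Section 3.2 also asks for a real prospect of going back to work, which suggests that people away from work predominate. The 40% rows then have little textual support. The in-danger group is still expressly admitted.

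**The harm depends on an assumed imbalance.** This stands. Nothing in the protocol says that lifestyle change differs by entry status. At 0.4 SD the term lowers the false-positive rate by only 0.1 to 2.8 points. At d = 0 it raises that of the ordinary test by 0.4 to 2.0 points.

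**Part of the power gain comes from a liberal test.** This also stands. The penalised fit was not simulated at d = 0. With the ordinary fit, power with the term differed by at most 2.0 points between d = 0 and d = 0.4. If the penalised fit behaves likewise, its power at d = 0 would differ from the unadjusted ordinary test by −1.5 points (58.8 − 60.3) to +5.2 points (49.5 − 44.3), but with the error rate controlled.

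**Conclusion.** The point holds. Section 3.9 leaves out a baseline variable that the study collects, that eligibility makes heterogeneous, and that is likely to predict the outcome strongly. The association can partly reflect who was already working, in a direction that depends on how lifestyle change differs by entry status. With no such difference, false positives are not inflated but power is lost: 44–61% against 59–69% with ordinary fits at n = 51 and an odds ratio of 2.5. These figures rest on assumed entry shares and retention rates, so they are illustrative.

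Three stronger readings are not supported:
- A reader might infer that the result will be biased, or biased towards no association. The protocol gives neither entry shares nor any difference in change, so neither the presence nor the sign of bias is known.
- A reader might infer that the omission always costs power. With the opposite sign the unadjusted test rejects more often, through confounding.
- A reader might infer that a baseline covariate separates keeping work from returning to it. It removes confounding by entry status, but the outcome categories stay as they are.

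The change is worth making before analysis; the omission does not invalidate the study.

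**What to change.** In section 3.9:

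1. Add baseline work status (working or not working) as one binary covariate in the main model. Code it by the section 2 definition as far as the ARR form allows, with the same coding at follow-up. State the reference period, since baseline falls in the four-week stay.
2. Specify a Firth-type penalised fit with penalised likelihood-ratio tests in advance, not only if a cell turns out empty, because sparse cells are to be expected at 51 to 59 people.
3. Show the baseline-by-follow-up table of work status.
4. Show an analysis of those not working at entry as a companion, so that returning to work can be seen on its own. An ordinary likelihood-ratio test there was liberal (7.0–10.8%), so it should not replace the main model.

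**Cost.** Two more parameters in the three-category model (8 to 10), sparse cells, and a check of whether the ARR form supports the 28-day coding. No new visit or form is needed.

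### Section 3.9 codes the primary outcome without reference to section 2's definition and leaves students no category; separately, the 80 percent power in section 3.10 is for before-after change, not for the primary association

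*Protocol*

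**What the plan says.** **Outcome.** Section 2 gives a study-wide definition: "Work participation defined in this study is working full time or partial with an employer, permanent or temporary or as a student". It adds a condition: "The employee has to work coherently in 28 days without to receive social benefits". Section 3.9 sets Y = work for the main issue, with physical activity, diets and life quality as predictors in a logistic regression, and splits Y as follows: "Work divides into three categories; a) full time working, b) part time working, c) not working". It mentions neither students, nor the 28 days, nor benefits, and does not refer back to section 2.

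**Primary question.** Section 2 asks: "What correlation is there between life style changing and work participation after participating in occupational rehabilitation on Muritunet".

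**Sample size.** Section 3.10 states that the research question is leading. It then gives three calculations for change between baseline and the end of the intervention, at p = 0.05 and 80 percent power:

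| Target | Participants | Stated power |
|---|---|---|
| Work participation, 25 percent increase | 51 | 80.4% |
| Weight, 11 kg reduction | 59 | 80.2% |
| Quality of life (15D), change of 0.02 | 55 | 80.7% |

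**The concern.** The primary outcome is described twice with different content. Two analysts could both follow the protocol and code the same participant differently, and the regression estimates would differ accordingly.

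The power figure raises a separate problem. Because section 3.10 ties the sample size to the research question, a reader may take the 80 percent to cover the link between lifestyle change and work. If it does not, a null result for the primary question could be over-interpreted as evidence of no association.

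**Working it through.** **Part 1: the two descriptions side by side**

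| Participant | Section 2 | 3.9 taken literally | 3.9 with section 2 read in |
|---|---|---|---|
| Full time, 28 days, no benefit | participating | a | a |
| Part time, 28 days, no benefit | participating | b | b |
| Part time, with a benefit | not participating | b | c |
| Student, no job | participating | c by default | no category fits |
| Student with a part-time job | participating as a student | b | b only if the 28-day rule is met or does not apply |
| No work, not a student | not participating | c | c |

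The third row is settled once section 2 governs section 3.9. The fourth is not: such a student participates, so c is wrong, but works neither full time nor part time. The fifth stays open because the 28-day condition names only the employee.

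Can work combined with a benefit occur? Two exclusions in section 3.2 limit it at entry: "People who receive work assessment allowance" and "People with or wants so seek for disability benefits". Sick leave, however, is a route into the study: "the participants have to be on sick leave or be in danger to be on sick leave". Benefits are also recorded later. Section 3.1 says of the register step: "Data collected are social benefits as sick leave, work assessment allowance, disability benefits, unemployment benefits". So the case can arise at follow-up. The protocol gives no count for it, nor for students.

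**Part 2: what the 80 percent covers**

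*The plan's own figure.* The 51 participants and 80.4% cannot be reproduced from the printed inputs, because the baseline rate and the share of people changing status are not given. They can be reached under unstated inputs. Assume that work is yes/no, the increase is 25 percentage points, the test is McNemar's (two-sided 5%, normal approximation), and a share D of participants changes status:

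power = Φ[(0.25·√51 − 1.96·√D) / √(D − 0.25²)]

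With D = 0.42: (1.785 − 1.270) / 0.598 = 0.862, so power is about 80.5%. The 51 is therefore attainable, but as power for a change in the work rate.

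*Why this does not carry over.* Power for change depends on the net shift and on how many people change status. Power for the association depends on how the outcome splits, on the spread of the predictors and on their correlation. Work participation could rise by 25 points with no relation to anyone's change in activity, diet or life quality. Of the other two calculations, weight is not in the primary model at all, and quality of life enters it only as a predictor. Section 3.10 gives no odds ratio, correlation or category split.

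*Illustration of association power.* None of these inputs is in the protocol: outcome collapsed to working yes/no, odds ratio (OR) per SD of one predictor, share working p from 0.25 to 0.75, R² of that predictor on the others from 0 to 0.2, two-sided 5%, no losses.

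power = Φ[√(N·p(1−p)·(1−R²))·ln OR − 1.96]

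- Best case (N = 51, p = 0.5, R² = 0, OR 2.0): √12.75 = 3.571; 3.571 × 0.693 − 1.96 = 0.515; power 70%.
- Worst case (p = 0.25 or 0.75, R² = 0.2): √7.65 = 2.766; 2.766 × 0.693 − 1.96 = −0.043; power 48%.
- OR for 80% power: exp(2.80 / 3.571) = 2.19 and exp(2.80 / 2.766) = 2.75.

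A simulation of the same yes/no outcome used three predictors, 50% or 70% working, predictor correlation 0 or 0.3, and a likelihood-ratio test calibrated to 5%, with 2,500 runs per setting. It gave 45-59% power at OR 2.0, and 80% power at an OR of 2.49 to 3.14. The two methods together span about 45-70% power at OR 2.0, and an OR of about 2.2-3.1 for 80% power.

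**The case against.** **Section 2 already governs.** Its definition is announced for the whole study, and section 3.9 opens by naming the same construct, so reading the definition into the three categories is natural. That stands for the benefit condition. A reader might infer a flat contradiction between the two sections; the text does not support that, because an omission with a reasonable reading is not a contradiction. The reading does not place students.

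**Section 3.10 never claims power for the regression.** Its figures sit under a heading about change, the time points are named, and section 3.9 describes the aim as exploratory. This is fair, and the risk of misreading is modest. But the sentence that ties the sample size to the research question is still wrong for a primary question about correlation.

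**Some detail belongs in an analysis plan.** The data source for the 28 days, a sensitivity analysis, the exact form of the logistic model and a detectable odds ratio may all be in a plan that is not shown. That stands, and their absence is not held against the protocol. What remains is what the protocol itself fixes in two different ways or describes incorrectly.

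**The odds ratios rest on assumptions.** They do, and a yes/no outcome is not the three-category outcome in section 3.9. They indicate scale only.

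**Conclusion.** Both parts hold and should be corrected.

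1. The primary outcome is incompletely fixed. Students count as participating in section 2 but have no category in section 3.9, and the benefit condition carries over only if the reader supplies the link. The number of participants affected is unknown.
2. The stated 80 percent is power for before-after change, not for the primary association. This follows from the text alone. The size of the gap depends on assumptions: with 51 people and a yes/no outcome, about 45-70% power at an odds ratio of 2.0 per SD.

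Two stronger inferences are not supported. A reader might conclude that 51 is miscalculated, because the printed interval of 18.05 to 31.95 (half-width 6.95) would imply power above 99.9% if it were the precision expected with 51 people. But section 3.10 bases the calculation on an earlier group whose size is not given, so the interval may belong to that group, and 51 is attainable as shown. A reader might also conclude that the study is too small for its primary question. The protocol states no target association, so that cannot be shown.

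**What to change.** **Outcome.** Make sections 2 and 3.9 use one definition. In 3.9, refer to section 2, so that a and b are full-time and part-time participation as defined there (for employees, 28 continuous days without social benefits) and c is not participating as defined there. Assign students without employment to a stated participating category, code employed students by one stated rule, and say whether the 28-day condition applies to students. Category c should not be worded as everyone else, since that would turn non-employed students into non-participants against section 2. If part-time work with a benefit is meant to count as b, change section 2 instead.

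**Sample size.** In 3.10, replace the sentence that says the research question leads with: *The sample size is based on before-after change in work participation, weight and quality of life. It is not a power calculation for the primary association.*

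**Cost.** No change in the sample size and no extra participants. Work status and social benefits are already listed at baseline, T1 and T2, and the registers add benefits, employment and education. The protocol does not say that any source records student status or 28 consecutive benefit-free days, so the sponsor should check that the chosen rule can be applied. The benefit condition may thin category b, and the power statement for the primary question becomes less favourable.
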